5.2. Exclusion Criteria

Subjects meeting any exclusion criterion for this study will be excluded from this study:

1. Active LN on induction therapy, or induction therapy completed within 12 weeks prior to Screening (stable maintenance therapy with mycophenolate or azathioprine allowed).
2. Active neuropsychiatric SLE, including, but not limited to, the following: seizure, new or worsening impaired level of consciousness, psychosis, delirium or confusional state, aseptic meningitis, ascending or transverse myelitis, chorea, cerebellar ataxia, mononeuritis multiplex, or demyelinating syndromes.
3. Primary diagnosis of autoimmune or rheumatic disease other than SLE (secondary Sjögren's syndrome or autoimmune thyroiditis are not exclusionary) or drug-induced lupus.
4. History of chronic, recurrent (3 or more of the same type of infection in 1 year) or recent serious infection (eg, pneumonia, septicemia), including viral infections, as determined by the investigator, or requiring anti-infective treatment within 12 weeks prior to Screening.
5. History of severe herpes infection (eg, herpetic encephalitis, ophthalmic herpes, or disseminated herpes) or signs of herpes or varicella zoster viral infection (chicken pox, shingles, or herpes zoster) within 12 weeks prior to Screening.
6. Positive COVID-19 test (either molecular, based on polymerase chain reaction [PCR], or antigenic) at Screening or symptoms suggestive of SARS-CoV-2 infection (such as fever, chills, cough, shortness of breath, fatigue, myalgia, headache, new loss of taste or smell, sore throat, nasal congestion, rhinitis, nausea, vomiting, or diarrhea) or close contact with an individual with SARS-CoV-2 infection within 2 weeks prior to randomization.
7. History of malignant disease within the 2 years before Screening or ongoing at the time of Screening, except basal cell carcinomas and squamous cell carcinomas of the skin, or completely excised carcinoma in situ of the cervix.
8. Chronic kidney disease with significant proteinuria (ie, >2 g/24 h or urine protein to creatinine ratio >200 mg/g) or decreased renal function (estimated glomerular filtration rate [eGFR] <30 mL/min).
9. New York Heart Association class III or IV congestive heart failure.
10. Concomitant disease or condition that could interfere with, or treatment of which might interfere with, the conduct of the study, or that would, in the opinion of the investigator, pose an unacceptable risk to the subject in this study.

11. Treatment with SLE SOC medications, except for the following, which are allowed: oral prednisone (or equivalent at a maximum of 20 mg/d); antimalarials at SOC dose (maximum: hydroxychloroquine 400 mg/d, chloroquine 250 mg/d, quinacrine 100 mg/d); methotrexate (maximum 25 mg/wk); leflunomide (maximum 20 mg/d); mycophenolate (mycophenolate mofetil [MMF] maximum 3000 mg/d or mycophenolic acid sodium [MPS] maximum 2160 mg/d); azathioprine (maximum 200 mg/d); and tacrolimus (maximum 3 mg/d). These medications are allowed as long as they were initiated at least 12 weeks prior to randomization, have been stable for at least 4 weeks prior to randomization, and will remain stable for the duration of the study. Subjects who are not planning to continue these medications during the study must have discontinued them at least 4 weeks prior to randomization.
12. These medications are prohibited as follows:
 - Topical corticosteroids and other topical immunosuppressive agents, including topical calcineurin inhibitors, within 2 weeks prior to randomization (Day 1)
 - Intralesional corticosteroids, IV, intramuscular (IM), and intra-articular corticosteroids within 4 weeks prior to randomization (Day 1)
 - Cyclosporine, voclosporin, pimecrolimus, and sirolimus within 4 weeks prior to randomization (Day 1)
 - Cyclophosphamide within 24 weeks prior to randomization (Day 1)
 - IV Ig or plasmapheresis within 12 weeks prior to randomization (Day 1)
 - All biologic agents, including anti-B-cell antibodies (eg, rituximab, ocrelizumab, and belimumab), other antibodies (eg, anifrolumab, adalimumab, and tocilizumab), Fc constructs (eg, abatacept and etanercept), cytokines, and live vaccines within 12 weeks prior to randomization (Day 1)
13. History of suicide attempt or suicidal ideation within 1 year prior to Screening.
14. History of substance abuse within 6 months prior to Screening or a urine drug test at Screening resulting positive for amphetamines, barbiturates, benzodiazepines, cannabinoids, cocaine, and opiates. Medical marijuana may be used per discretion of the investigator.
15. History or positive test result for human immunodeficiency virus (HIV) at Screening.
16. Active hepatitis B virus (HBV) infection determined at Screening as positive test result for hepatitis B surface antigen.
17. Active hepatitis C virus (HCV) infection determined at Screening as HCV ribonucleic acid (RNA) above the limit of detection in subjects with positive HCV antibody titer.
18. History of, or ongoing, active tuberculosis (TB) or untreated latent TB infection (LTBI), determined by a positive QuantiFERON-TB Gold or positive or borderline T-SPOT (Elispot) test performed locally at Screening. Subjects with documented previously completed appropriate LTBI treatment and without evidence of re-exposure will not be required to be tested. Indeterminate QuantiFERON-TB Gold or T-SPOT tests may be repeated once; it will be considered positive if retest results are positive or indeterminate.

19. Any other significant condition (eg, medical, psychiatric, or social) that according to the investigator's judgment would prevent compliance with study protocol and full study participation.
20. Subjects must not be participating in another investigational study or have participated in an investigational study within the past 30 days prior to randomization (Day 1).
21. History of or current inflammatory skin disease other than SLE that in the opinion of the investigator could interfere with the inflammatory skin assessments and confound the disease activity assessments.
22. History of any non-SLE disease that had required treatment with oral or parenteral corticosteroids for more than a total of 2 weeks within the last 24 weeks prior to randomization.

5.3. Screening Failures, Rescreening, and Subject Replacement

Rescreening is permitted after consultation with the Sponsor if a subject fails initial screening. Rescreening may occur only once. The subject identification number will remain the same at the time of rescreening. The initial screening information and the reason why the subject failed this screening will be recorded in EDC. If the subject also fails rescreening, rescreening information and reason for failure will similarly be recorded in EDC.

Subjects who discontinue the study may be replaced after consultation with the Sponsor.

6. STUDY DRUG(S)

6.1. Study Drug(s) Description

Table 6.1 describes the formulation, dose, regimen, duration, packaging, and labeling of the study drug and placebo.

Table 6.1: Study Drug Dosing Information

Study Drug Name	DS-7011a
Dosage Formulation	Provided as sterile solution in vials of 2 mL at a concentration of 100 mg/mL
Dosage Level	20 mg/kg
Route of Administration	Intravenous
Dosing	Intravenous infusions over 1 hour once every 4 weeks on Day 1, Day 29, and Day 57
Duration	Once every 4 weeks for 8 weeks (Weeks 0, 4, and 8)
Packaging	Glass vials/carton Packaging will clearly display the name of product, storage condition, and other required information as applicable in accordance with local regulations.
Labeling	Vials will be labeled as required per local regulatory requirement.
Source	DS-7011a will be supplied by the Sponsor.

DS-7011a will be provided as a sterile solution in vials of 2 mL at a concentration of 100 mg/mL and will be infused diluted in dextrose 5% in water (D5W). Placebo will be prepared using D5W or normal saline as a possible alternative. DS-7011a and placebo will be administered by IV infusion. DS-7011a will be given at the dose of 20 mg/kg q4w IV. The DS-7011a dose was selected based on the safety, tolerability, PK, and PD results of the DS-7011a FIH Phase 1a study. The intent is to select the optimal dose that is found in Phase 1a to be safe, well tolerated, and maximally active pharmacodynamically.

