6.2. Preparation, Handling, Storage, and Accountability for Study Drug

6.2.1. Preparation, Handling, and Disposal

The preparation of study drug will be conducted in accordance with the Dose Preparation Instructions (DPI) provided by the Sponsor.

Procedures for proper handling and disposal should be followed in compliance with the standard operating procedures (SOP) of the site.

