6.3.2. Blinding/Unblinding

Subjects, investigators, and site staff will be blinded, except for the unblinded site pharmacist or designee who will be responsible for preparing the study drugs. Sponsor's staff or representative (eg, CRO) will also be blinded. Two cases of unblinding are contemplated: one due to medical emergency and one accidental. In the case of an emergency where, in the opinion of the investigator, discontinuation of study drug is not sufficient, and the study drug must be unblinded in order to further evaluate a course of medical treatment, the Principal Investigator (PI) is authorized to perform the unblinding.

The unblinded subject will discontinue treatment and study participation and will be informed about the treatment assigned. Information about the treatment assignment must be restricted to designated site staff/personnel who are providing immediate care to the subject. Any documentation of the treatment assignment must be maintained separately (ie, in a secured file). The information must not be included in the subject's source files to ensure the treatment assignment will remain blinded to study personnel not involved with the subject's immediate care. In the case of accidental unblinding, the unblinded subject may complete the study.

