8.8.1.8. Overdose

An overdose is defined as the accidental or intentional administration of any dose of a product that is considered both excessive and medically important. All occurrences of overdose must be reported to the Sponsor within 24 hours of awareness.

Overdose will be reported via eCRF. An "excessive and medically important" overdose includes any overdose in which either an SAE or a non-serious AE (Section 8.8.1), or no AE occurs and is considered by the investigator as clinically significant, ie, poses an actual or potential risk to the subject.

Occupational exposures must be reported via EDC.

Overdoses are not expected in this study in which the study drug is monitored at all times by the clinical site staff. The pharmacist and the pharmacy staff are responsible for correctly preparing the study drug for delivery by the staff to the subjects.

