9.2. Sample Size Determination

The study will enroll up to 24 subjects with SLE in 2 parallel arms randomized to receive 2:1 DS-7011a or placebo. Tentatively, 9 of these 24 subjects will be of African descent. Also, tentatively, 9 of these 24 subjects will be positive for anti-Sm and/or anti-RNP autoantibodies.

The sample size selected is not based on statistical power considerations. The number of subjects in each arm is considered sufficient to achieve the objectives of this study. Initial evidence of DS-7011a efficacy will be inferred by the impact DS-7011a shows on clinical endpoints, mainly CLASI-A, and several mechanistic endpoints. This impact will be evinced by comparing endpoint values between DS-7011a-treated and placebo-treated subjects and between pretreatment (baseline) and post-treatment time points. Concomitant and consistent impact on multiple endpoints will be initial evidence of efficacy, especially if this impact is of large extent. DS-7011a extent of impact will be compared to that reported for antibodies approved (belimumab and anifrolumab) or in late phase of development (BIIB059) for the treatment of SLE². The result of this comparison will inform a DS-7011a “go/no-go” decision to further development.

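### DS-7011a is diluted only in D5W but placebo may be in D5W or normal saline, so the diluent can reveal assignment unless it is concealed

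*Combined protocol and SAP*

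**What the plan says.** Section 6.1 of the protocol says that DS-7011a "will be infused diluted in dextrose 5% in water (D5W" and gives no other option. The next sentence reads: "Placebo will be prepared using D5W or normal saline as a possible alternative". The synopsis (Section 1.1) carries the same two statements.

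On blinding, Section 6.3.2 states: "Subjects, investigators, and site staff will be blinded, except for the unblinded site pharmacist or designee". Sponsor staff and their representatives are also to be blinded. Section 8.8.1.8 makes the pharmacy responsible for "correctly preparing the study drug for delivery by the staff to the subjects", so people other than the preparer handle the finished infusion.

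The only labelling rule in Section 6.1 concerns the vials and their packaging: "Vials will be labeled as required per local regulatory requirement". Section 6.2.1 refers preparation to a separate document ("in accordance with the Dose Preparation Instructions (DPI) provided by the Sponsor"), and Section 6.2.3 refers to the Pharmacy Manual for storage of the infusion solution. No section mentions a bag cover, a neutral bag label, or a common diluent for the two arms.

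Section 4.2 relies on blinding and randomization as the protection against bias. Section 9.2 gives the size: "The study will enroll up to 24 subjects with SLE in 2 parallel arms randomized to receive 2:1 DS-7011a or placebo". It also says that the comparison with placebo, among other inputs, will inform the decision on further development.

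**The concern.** Under the written rule the diluent depends on the arm. Saline is open to placebo only, so anyone who learns that a subject received saline knows the assignment. That person need not be the unblinded preparer; it could be the staff member giving the infusion, the investigator or the subject.

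What is at stake is the judgement-based part of the assessment:

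- CLA-IGA, PGA-SLE and CGI-C are rated by the investigator (Sections 8.6.3, 8.6.5, 8.6.6).
- The patient-reported outcomes are rated by the subject (Section 8.6.7).
- Adverse event causality, which feeds the primary safety objective, is the investigator's judgement (Section 10.4.5).
- The mucosal and hair-loss parts of CLASI-A come from the site (Section 8.6.2).

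Knowledge gained at one infusion persists through every later visit, and PGA-SLE asks the assessor to look back at the previous mark. Section 6.3.2 lets an accidentally unblinded subject complete the study, and Section 9.5.1 does not say how such a subject's data are to be treated. The trial tests no hypothesis (Section 9.1), but that does not remove the problem, because the evidence is the size and consistency of descriptive differences between arms.

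**Working it through.** The plan gives no figure for this point, so there is none to reproduce. The check has two parts.

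**1. Reading the sections together.** Sections 1.1 and 6.1 allow {D5W} for active and {D5W, saline} for placebo. Section 6.3.2 blinds everyone at the site except the preparer. The two are compatible only if saline is never used or blinded people cannot learn the diluent. The protocol requires neither.

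**2. What the diluent reveals.** Inputs:

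- Allocation 2:1 and N up to 24 (Section 9.2): 24 × 2/3 = 16 active and 24 × 1/3 = 8 placebo.
- s = share of placebo prepared in saline. The documents do not give it, so the full range 0 to 1 is shown.
- Assumption: the diluent is visible to blinded people.

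By Bayes' rule:

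- P(placebo | saline) = 1 for any s > 0, because active is never in saline.
- P(active | D5W) = (2/3) / [(2/3) + (1/3)(1 − s)] = 2/(3 − s).
- Expected placebo subjects identified, if each keeps one diluent throughout: 8s.
- Expected placebo subjects identified at least once, if the diluent varies independently over the 3 infusions: 8 × [1 − (1 − s)³].

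| s (assumed) | P(active given D5W) | Identified of 8, fixed diluent | Identified of 8, varying diluent |
|---|---|---|---|
| 0 | 0.667 | 0 | 0 |
| 0.10 | 0.690 | 0.8 | 2.2 |
| 0.25 | 0.727 | 2 | 4.6 |
| 0.50 | 0.800 | 4 | 7.0 |
| 0.75 | 0.889 | 6 | 7.9 |
| 1 | 1.000 | 8 | 8 |

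At s = 1 every D5W infusion is active, so all 24 assignments can be read off. If both arms had the same options in the same proportions, or the diluent were fully hidden, the probabilities would stay at the 2:1 prior of 0.667 and 0.333.

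**Illustration of scale only.** Suppose that identification shifts a subjective score by d = 0.3 to 0.5 SD in identified placebo subjects and changes nothing else. Both d and s are assumed.

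- Shift in the placebo mean = s × d: 0.25 × 0.3 = 0.075 SD to 0.50 × 0.5 = 0.25 SD.
- Standard error of the difference between arms = √(1/16 + 1/8) = 0.433 SD.
- Ratio: 0.075/0.433 = 0.17 to 0.25/0.433 = 0.58 standard errors. At s = 0 the shift is zero.

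**The case against.** The strongest reply is that the safeguard may exist elsewhere. Saline is only a possible alternative and may never be used. The Dose Preparation Instructions and Pharmacy Manual could specify bag covers or neutral labels, and the unblinded preparer could apply them. The protocol does not say that the diluent appears on the bag or in records that blinded staff see. This stands: the text does not show that the blind is broken, only that it can be. It does not dispose of the point, because the protocol itself sets different diluent rules for the two arms and claims blinding without stating what conceals the difference.

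A second reply is that the main efficacy measure is shielded. Section 9.2 puts most weight on CLASI-A, and Section 8.6.2 has central reviewers generate that score from photographs. Safety laboratory tests, immunoglobulins, autoantibodies, complement, gene signatures and skin mRNA leave little room for rater judgement. This also stands, and it limits the concern to the endpoints listed above.

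A third is that the summary of changes can be read as allowing either diluent for either product. A change log is not the operative text. If that was the intention, Sections 1.1 and 6.1 do not express it and need correcting.

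A reader might also infer that the leak runs one way, exposing placebo only and so favouring the drug. The documents do not support that. Once saline is used, D5W becomes informative about active treatment. An investigator who knows that a subject is on placebo may also be less ready to call an event drug-related, which would make DS-7011a look worse on safety.

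**Conclusion.** The point holds as a conditional one: the stated diluent rules can reveal assignment to people who are meant to be blinded, unless the diluent is concealed. If saline is used and seen, identification of placebo is certain. The inference from D5W to active strengthens from 0.667 to 0.73 at a 25% saline share and 0.80 at 50%, and at those shares 2 to 4 of about 8 controls are identified if each keeps one diluent throughout. Both shares are assumptions, and zero is equally compatible with the text.

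The size of any bias cannot be determined from the documents. The range of 0.17 to 0.58 standard errors rests wholly on assumed inputs and is not an estimate. The direction may differ between efficacy ratings and adverse event causality. The conclusion that the double blind is in fact broken, or that the centrally read CLASI-A is compromised, would go beyond what the text shows.

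**What to change.** Reconcile Sections 1.1 and 6.1 with Section 6.3.2 in one of two ways:

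- Give both arms the same diluent options and require that the choice be made independently of allocation, for example one diluent per site for both arms.
- If the options must differ, require in the protocol that the infusion bag, and any record seen by blinded people, conceal the diluent.

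Either route is sufficient. Which diluent is suitable is for the sponsor to decide. If the Dose Preparation Instructions or Pharmacy Manual already require concealment, Section 6.3.2 should say so.

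The cost is a sentence or two in the protocol, alignment of the preparation instructions and, on the second route, bag covers and neutral labels. The downside of the first route is that sites may lose some flexibility in preparing placebo.

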6.2. Preparation, Handling, Storage, and Accountability for Study Drug

6.2.1. Preparation, Handling, and Disposal

The preparation of study drug will be conducted in accordance with the Dose Preparation Instructions (DPI) provided by the Sponsor.

Procedures for proper handling and disposal should be followed in compliance with the standard operating procedures (SOP) of the site.

6.2.2. Drug Administration

DS-7011a or placebo will be administered by IV infusion over 1 hour.

6.2.3. Storage

DS-7011a must be stored in a secure, limited access storage area under the recommended storage conditions noted on the label and protected from light. If storage conditions are not maintained per specified requirements, then the Sponsor or contract research organization (CRO) should be contacted.

See the Pharmacy Manual for additional information on storage conditions of study drug/storage conditions of the infusion solution.

6.2.4. Drug Accountability

When a drug shipment is received, the investigator or designee will check the amount and condition of the drug against the shipping documentation.

The Receipt of Shipment Form should be transmitted as instructed on the form. The original will be retained at the study site.

In addition, the investigator or designee shall contact the Sponsor as soon as possible if there is a problem with the shipment.

The investigator is responsible for study drug accountability, reconciliation, and record maintenance (ie, Receipt of Shipment Form, dispensation/return record, and certificate of destruction/return receipt).

All used study drug will be destroyed at the site after reconciliation. Unused study drug will be destroyed at the site unless the Sponsor authorizes the study drug to be returned.

6.3. Measure to Minimize Bias: Randomization and Blinding

6.3.1. Method of Treatment Allocation

Randomization will follow a randomization schedule generated by an independent biostatistician.

6.3.2. Blinding/Unblinding

Subjects, investigators, and site staff will be blinded, except for the unblinded site pharmacist or designee who will be responsible for preparing the study drugs. Sponsor's staff or representative (eg, CRO) will also be blinded. Two cases of unblinding are contemplated: one due to medical emergency and one accidental. In the case of an emergency where, in the opinion of the investigator, discontinuation of study drug is not sufficient, and the study drug must be unblinded in order to further evaluate a course of medical treatment, the Principal Investigator (PI) is authorized to perform the unblinding.

The unblinded subject will discontinue treatment and study participation and will be informed about the treatment assigned. Information about the treatment assignment must be restricted to designated site staff/personnel who are providing immediate care to the subject. Any documentation of the treatment assignment must be maintained separately (ie, in a secured file). The information must not be included in the subject's source files to ensure the treatment assignment will remain blinded to study personnel not involved with the subject's immediate care. In the case of accidental unblinding, the unblinded subject may complete the study.

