4.1.2. End of the Study

The primary completion date is the date when the last subject is examined or receives an intervention for the purposes of final collection of data (database lock) for all outcome analyses (ie, the last subject's Final Visit [Day 113]). The global end of the study is the last subject's

Follow-up Visit (Day 169) (ie, the last subject's last visit overall). The study may be discontinued by the Sponsor for other reasons (ie, administrative, program-level or class-related), in which case the global end of the study would be the date the Sponsor discontinues the study.

The subject's End of Study (EOS) Visit is the date of their last study visit/contact. The scheduled EOS Visit on Day 169 will be by telephone unless there is the need to collect blood samples.

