7. STUDY DRUG DISCONTINUATION AND DISCONTINUATION FROM THE STUDY

7.1. Discontinuation of Study Drug

The primary reason for the permanent discontinuation of DS-7011a treatment administration must be recorded. Reasons for treatment discontinuation include:

- Completed
- Death
- AE
- Withdrawal by Subject (**to discontinue study drug**) NOTE: in this section this is only withdrawal for treatment with study drug and is NOT the same thing as a complete withdrawal from the study. Discuss with the subject that they will remain in the study (ie, continue with study visits and assessments).
- Physician Decision
- Lost to Follow-up (see Section 7.4 for details on when a subject is considered Lost to Follow-up)
- Pregnancy
- Protocol Deviation
- Study Termination by Sponsor
- Other

After study drug is permanently discontinued for any reason other than death or lost to follow-up, the subject will be treated as clinically indicated by the investigator or referring physician.

The investigator must discuss with the subject that their decision to permanently discontinue the study drug means the subject still agrees to continue into the Follow-up Period for onsite or modified follow-up visits. Subjects will be followed at regularly scheduled intervals (see [Table 1.1](#)).

Procedures for Discontinuation from Study Drug

The subject should be instructed to contact the investigator or study site staff before or at the time study drug is discontinued.

If a subject is discontinued from the study drug:

- The reason(s) for discontinuation and the last dose date should be documented in the subject's medical record and eCRF.
- Due to an AE, the investigator will follow the subject until the AE has resolved or stabilized.

- An EOT evaluation should be performed as described in the Schedule of Events (SoE) (Table 1.1).
- A safety follow-up evaluation should be performed approximately 30 days after the last dose of study drug as described in the SoE (Table 1.1).

The investigator will complete and report the observations as thoroughly as possible up to the date of discontinuation, including the date of last dose. All procedures specified for the EOT visit will be conducted. See Table 1.1 for specific EOT procedures.

If a subject does not agree to continue to come to the study site, then a modified follow-up must be arranged to ensure the continued collection of endpoints and safety information. Options for modified follow-up are noted below.

Modified Follow-up Options

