The following modified follow-up options can be offered to the subject who does not agree to study visits at the study site.

- Study personnel contacting the subject by telephone (may be quarterly, bi-annually, annually, or only at EOS)
- Study personnel contacting an alternative person (eg, family member, spouse, partner, legal representative, physician, or other healthcare provider)
- Study personnel accessing and reviewing the subject's medical information from alternative sources (eg, doctor's notes, hospital records)

Dates of the modified follow-up contact(s) should be recorded. See Section 7.2 for definition of withdrawal by subject from the study (ie, withdrawal of consent).

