8.8.1. Adverse Events

8.8.1.1. Methods to Detect Adverse Events

The definitions of an AE or SAE can be found in Section 10.4. AEs may be directly observed, reported spontaneously by the subject or by questioning the subject (or, when appropriate, by a caregiver, surrogate, or the subject's legally authorized representative) at each study visit. Subjects should be questioned in a general way, without asking about the occurrence of any specific symptoms. The investigator must assess all AEs to determine seriousness, severity, and causality. The investigator and any qualified designees are responsible for detecting, documenting, and recording events that meet the definition of an AE or SAE and remain responsible for following AEs that are serious, considered related to the study drug or study procedures, or that caused the subject to discontinue.

All clinical laboratory results, vital signs, and ECG results or findings should be appraised by the investigator to determine their clinical significance. Isolated abnormal laboratory results, vital sign findings, or ECG findings (ie, not part of a reported diagnosis) should be reported as AEs if they are symptomatic, lead to study drug discontinuation, require corrective treatment, or constitute an AE in the investigator's clinical judgment.

Medical conditions (including laboratory values/vital signs that are out of range) that were diagnosed or known to exist prior to informed consent will be recorded as part of medical history. COVID-19 assessments are detailed in Section 8.8.2.

8.8.1.2. Time Period for Collecting Adverse Events, including Adverse Events of Special Interest and Serious Adverse Events

For all randomized subjects, all AEs occurring after the subject signs the ICF and through the EOS Visit, whether observed by the investigator or reported by the subject, will be recorded as detailed in Section 10.1.6.2. All SAEs will be followed until resolution, stabilization, the event is otherwise explained, or the subject is lost to follow-up.

Medical conditions (including clinically significant laboratory values/vital signs that are out of range) that were diagnosed or known to exist prior to the consent date will be recorded as medical history, and not an AE. Exacerbation of a pre-existing medical condition or symptom, including increase in severity of the symptom will be recorded as an AE.

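### Emergency unblinding ends study participation as well as treatment, so collection of new AEs and AESIs can stop before the planned Day 169 contact

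*Combined protocol and SAP*

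**What the plan says.** Section 6.3.2 provides for two kinds of unblinding. For a medical emergency the rule is: "The unblinded subject will discontinue treatment and study participation and will be informed about the treatment assigned". A subject unblinded by accident, however, may complete the study. The same section limits who may know the assignment: "Information about the treatment assignment must be restricted to designated site staff/personnel who are providing immediate care to the subject".

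Section 8.8.1.2 sets the AE collection window: "For all randomized subjects, all AEs occurring after the subject signs the ICF and through the EOS Visit" are to be recorded. Section 4.1.2 says that a subject's "End of Study (EOS) Visit is the date of their last study visit/contact", and footnote a of Table 1.1 repeats this.

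Section 7.1 covers subjects who stop study drug but remain in the study: "Subjects will be followed at regularly scheduled intervals". It also requires an EOT evaluation and states: "A safety follow-up evaluation should be performed approximately 30 days after the last dose of study drug". Subjects unwilling to attend the site can be offered modified follow-up, including telephone contact.

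For events already known, Section 8.8.1.1 says that investigators "remain responsible for following AEs that are serious, considered related to the study drug or study procedures", or that caused discontinuation. Section 8.8.1.2 has SAEs followed to resolution or stabilization. Section 7.3 does the same for an AE that led to withdrawal, and requires early termination (ET) procedures.

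**The concern.** The primary objective is safety and tolerability, and the AESIs are infections (herpes zoster and respiratory tract infections, including COVID-19). Section 4.1.1 follows other subjects to Day 113, when exposure and activity are expected to have declined, and then by telephone to Day 169 for SAEs, AEs and AESIs.

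The rule in 6.3.2 takes out of that follow-up a subject who has just had a medical emergency. The Safety Analysis Set (9.4.2) keeps every dosed subject and TEAEs are summarized as incidence (9.5.2.1). Such a subject would therefore stay in the denominator while later events might not be collected. Drug activity may outlast the last contact: in preliminary Phase 1a data in healthy subjects (2.3), ex vivo IL-6 inhibition still averaged 86% four weeks after one 20 mg/kg dose.

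**Working it through.** The plan gives no figure to reproduce on this point. The check is a reading of the text followed by day arithmetic.

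**Text**

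1. Section 6.3.2 ends treatment and participation after emergency unblinding.
2. Section 4.1.2 makes EOS the last visit or contact, so EOS moves forward when participation ends.
3. Section 8.8.1.2 collects AEs only through EOS, so the window for new events closes with it.
4. What remains is follow-up of known events (8.8.1.1, 8.8.1.2, 7.3), ET procedures (7.3) and possibly the 7.1 EOT and 30-day evaluations. None of these requires collection of new events up to Day 169.

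**Length of the gap**

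Inputs: dosing on Days 1, 29 and 57 (Table 6.1); final planned contact on Day 169 (4.1.1); safety evaluation about 30 days after the last dose (7.1). If that evaluation is the last contact, it falls on day L = dose day + 30, and the gap is 169 − L.

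| Last dose | L | Gap to Day 169 |
|---|---|---|
| Dose 1 (Day 1) | 1 + 30 = 31 | 169 − 31 = 138 days |
| Dose 2 (Day 29) | 29 + 30 = 59 | 169 − 59 = 110 days |
| Dose 3 (Day 57) | 57 + 30 = 87 | 169 − 87 = 82 days |

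An emergency on day E after that evaluation is itself a contact, so the gap is at most 169 − E. From Day 100 it is at most 169 − 100 = 69 days; from Day 150, at most 169 − 150 = 19 days. Later contacts to follow an ongoing event shorten any of these. If the 30-day evaluation is not held, the length depends on the dates of the ET procedures and of the last contact for the triggering event. The documents do not fix either date, so no figure is given for that case.

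**Against drug activity**

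Day 113, by which exposure and activity are expected to have declined, is 113 − 57 = 56 days after dose 3. A last contact at 30 days is 56 − 30 = 26 days short of that, and close to the four-week point of the IL-6 result.

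**The case against.** The strongest reply is that follow-up need not stop. Section 6.3.2 does not forbid safety contact. Section 7.1 attaches its EOT and 30-day evaluations to stopping drug. Section 7.2 does not list unblinding as a reason for leaving the study, and treats consent as withdrawn only when every follow-up method is refused. Section 8.8.1.2 covers all randomized subjects, and Table 1.1 puts the scheduled EOS Visit at Day 169. A site could keep telephoning the subject.

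This shows that the sections can be read together, but it does not remove the conflict. Section 6.3.2 states an explicit rule, 7.1 is written for subjects who remain in the study, and EOS is defined by the last contact, not by Day 169. Since 6.3.2 lets an accidentally unblinded subject complete the study, knowledge of the assignment is not in itself a reason to end follow-up.

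Three parts of the reply stand:

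- The trigger is narrow. Stopping drug must be insufficient and the assignment must be needed to decide treatment, in a trial of up to 24 subjects that tests no hypothesis.
- The IL-6 result is an ex vivo measure in healthy subjects. It suggests continuing activity but is not evidence of later infections.
- Because the investigator may perform the unblinding and also judges causality, AEs recorded afterwards are reported and assessed with the assignment known. The fix has to deal with this.

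A reader might also infer that the emergency itself goes unrecorded or unfollowed, or that all contact ends on the infusion day. The documents support neither: the triggering AE is followed until resolved or stabilized, and ET procedures are required.

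**Conclusion.** The point holds as a conflict in the plan worth correcting. Under 6.3.2, read with 4.1.2 and 8.8.1.2, collection of new AEs and AESIs can stop before Day 169 after an emergency unblinding, contrary to the approach in 7.1. The gap covers new, later events only.

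The 138, 110 and 82 days assume that the 30-day evaluation is held and is the last contact. They are not typical values, and emergencies after that evaluation give shorter gaps.

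A reader might go further and infer that the reported AE rates will be biased. The documents do not support that: they give no number of emergency unblindings, and it may be zero. The case for change is that the subjects affected would be those with a medical emergency, safety is the primary objective, and the change is small.

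**What to change.** Amend 6.3.2 so that emergency unblinding stops study drug only. The subject, flagged as unblinded, stays in scheduled follow-up to Day 113 and Day 169 unless consent is withdrawn. Where site visits are refused, use the 7.1 modified follow-up with at least the Day 169 call. That minimum should be explicit, because 7.1 leaves the timing of telephone contact open: "Study personnel contacting the subject by telephone (may be quarterly, bi-annually, annually, or only at EOS".

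Keep the existing restriction on assignment information. Flag the efficacy and PRO data recorded after unblinding, and also the AEs and their causality assessments.

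The cost is one amended sentence, a data flag, and visits already in Table 1.1: Days 85 and 113 and the Day 169 call after a dose 3 exit; at most Days 2, 8, 29, 57, 85 and 113 and that call after a dose 1 exit. The remaining limitation is that later assessments are not blinded, which flagging discloses but does not remove.

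As a separate labelling clarification, a footnote to Table 1.1 could say that the EOT procedures serve as the ET procedures cited in 7.3, since no column is labelled ET.
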